17.5.4.2. Analysis

For this outcome the rate ratio and 95% confidence intervals will be presented based on

Poisson regression.

17.5.5. Occurrence of 1 or more BSI

17.5.5.1. Derivation

BSI is as defined in section 17.4.1.1. Where there are multiple positive cultures in the POTW,

independent episodes of BSI will be classified as in section 17.5.3.1. If a baby has one or

more independent episodes of BSI within the POTW then this is classed as 'Yes'.

17.5.5.2. Analysis

The analysis will use the method of Fisher's exact test to compare proportions in the standard

group compared to the impregnated group and relative risks will be presented with 95%

confidence intervals.

17.5.6. Rate of catheter-related BSI per 1000 PICC days

17.5.6.1. Derivation

Catheter-related BSI is defined as "Yes" if the same organism is grown on the PICC-tip and blood/CSF sample. This information can found on CRF "Form 5: Microbiology" under "organism cultured". The total number of independent episodes of catheter-related BSI that occur when the line is in situ during the POTW should be calculated for each baby and then summed to find the total number of catheter-related BSI in each treatment arm. Where a baby has multiple positive cultures within the primary outcome time window they will be classified as single/multiple episodes of independent catheter-related BSI as in section 17.5.3.1.

The total number of days the PICC is in situ for during the POTW will be calculated using the derivation in section 17.5.4.1.

The rate of BSI per 1000 PICC-days is calculated as:

 $\frac{\textit{Total number of independent episodes of CR BSI that occur when line is in situ during POTW, across treatment arm}}{\textit{Total number of days PICC is in situ for during the POTW across treatment arm}}} \times 1000$

17.5.6.2. Analysis

For this outcome the rate ratio and 95% confidence intervals will be presented based on Poisson regression.

17.5.7. Rate of blood/CSF culture sampling per 1000 PICC days

17.5.7.1. Derivation

Each blood/CSF culture sample can be found on CRF "Form 5: Microbiology". The total number of these samples taken when the line is in situ during the primary outcome time window should be summed across each treatment arm.

Details on calculating the total number of days PICC is in situ for during the primary outcome time window can be found in section 17.5.4.1.

The rate of BSI per 1000 PICC-days is calculated as:

 $\frac{\textit{Total number of blood or CSF samples taken when the line is in situ during the POTW, across treatment arm}{\textit{Total number of days PICC is in situ for during the POTW across treatment arm}} \times 1000$

17.5.7.2. Analysis

For this outcome the rate ratio and 95% confidence intervals will be presented based on

Poisson regression.

17.5.8. Duration of antimicrobial exposure from randomisation up to 48 hours after line removal

17.5.8.1. Derivation

This can be found on CRF "Form 4: Daily follow-up". If "Yes" is selected for either "Were IV

antibiotics given?" or "Were IV or enteral antifungals given?" and "Prophylaxis" was not

selected for "If yes, were antifungals used for the following?", then the baby has antimicrobial

exposure for that day. The total number of days should be summed for each baby.

17.5.8.2. Analysis

The analysis will use the method of the two sample t test or Mann Whitney U test depending

on the distribution of the data. Means will be presented with 95% confidence intervals or

medians and interquartile range as appropriate.

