8.4. Patient population studied

The trial population aims to include 858 babies who require the narrowest PICC (Premicath 1

French gauge (Fr)).

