8.7. Method of assignment to treatment

Full details of the randomisation procedure can be found in sections 6.3 and 9.2 of the protocol.

The randomisation list will be generated by a statistician (who is not involved with the PREVAIL

trial) at the CTU. Babies will be randomised to AM-PICC or S-PICC in a ratio of 1:1.

Randomisation will be stratified by centre. Babies will be randomised using a secure (24-hour)

web based randomisation programme controlled centrally by the CTU to ensure allocation

concealment. Details of block sizes can be found in the Statistics Trial File under section 4.

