9.2. Secondary outcomes

Outcomes captured up until 48 hours after PICC removal:

1. Rifampicin resistance in any isolate from blood/CSF culture.

2. Rifampicin resistance in any isolate from PICC tips.

3. Type of organism isolated from BSI.

4. Rate of BSI per 1000 PICC-days (including recurrent BSI).

5. Occurrence of 1 or more BSI.

6. Rate of catheter-related BSI per 1000 PICC days.

7. Rate of blood/CSF culture sampling per 1000 PICC days.

8. Duration of antimicrobial exposure from randomisation up to 48 hours after PICC

removal.

9. Time to PICC removal.

Outcomes captured up until discharge home from neonatal care/death/6 months post

randomisation:

10. Chronic lung disease 36 weeks postmenstrual age.

11. Necrotizing enterocolitis (NEC): Bell's stage II or III.

12. Treatment for retinopathy of prematurity.

13. Abnormalities on cranial ultrasound.

14. Time to full milk feeds after randomisation.

15. Total duration of parenteral nutrition from randomisation until discharge from NNU.

16. Death:

a) within 6 months (26 weeks) of randomisation

b) before discharge home from neonatal care

c) time to death

10. Determination of Sample Size

The sample size calculation can be found in section 9.4 of the protocol.

11. Study Framework

The overall objective for each of the study outcomes (primary and secondary) is to test the

superiority of AM-PICCs compared with S-PICCs.

12. Confidence Intervals, p-values and Multiplicity

All applicable statistical tests will be two-sided and will be performed using a 5% significance

level; confidence intervals presented will be 95%. No adjustment will be made for multiplicity

for the secondary outcomes. Percentages will be presented as 1 decimal place. Test statistics,

p-values, confidence intervals and measures of spread will be presented as 2 decimal places.

13. Timing and Objectives of Interim and Final Analyses

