17.5.15.2. Analysis

The analysis will use the method of the two sample t test or Mann Whitney U test depending

on the distribution of the data. Means will be presented with 95% confidence intervals or

medians and interquartile range as appropriate.

The proportion of days in the primary outcome time window spent on parenteral nutrition will

be reported.

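### The two duration outcomes have no stated between-arm effect with a confidence interval, and none at all if the Mann-Whitney test is used

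*SAP*

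**What the plan says.** SAP sections 17.5.8.2 (antimicrobial exposure) and 17.5.15.2 (parenteral nutrition) use the same text for the test and the summaries. The test: "The analysis will use the method of the two sample t test or Mann Whitney U test depending". The sentence continues, and the summaries follow: "on the distribution of the data. Means will be presented with 95% confidence intervals or" "medians and interquartile range as appropriate".

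Neither section gives a criterion for choosing the test. Neither mentions a difference in means, a difference in medians or a shift between arms.

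Two general sections apply to all outcomes. Section 11 sets a superiority aim throughout: "The overall objective for each of the study outcomes (primary and secondary) is to test the" superiority of the impregnated line. Section 12 fixes the level ("All applicable statistical tests will be two-sided and will be performed using a 5% significance") and the width of intervals ("level; confidence intervals presented will be 95%. No adjustment will be made for multiplicity" for the secondary outcomes). It does not say what quantity each interval should describe, and it need not. That belongs in the outcome sections.

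**The concern.** A superiority comparison should end in an estimate of how much the arms differ and how precisely that is known. For these two outcomes the natural statement is the number of days saved or added, with an interval. As written, one branch may or may not give this, and the other does not.

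The branch without it is the one the data will probably select. Counts of days are bounded at zero and tend to have a long right tail, so a choice based on distribution leads to Mann-Whitney. The report would then hold two medians, two interquartile ranges and a p-value. A non-significant result could not be read as ruling out a difference of any particular size, and a significant one would carry no measure of precision.

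The two tests also compare different things: the t test compares means, and Mann-Whitney compares the ordering of values. Until one is named, the quantity being compared is open as well.

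**Working it through.** The SAP states no expected difference, standard deviation or power for these outcomes, so there is no figure to reproduce. The check is first a comparison of sections and then a simulation on assumed shapes.

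**1. What each type of tested outcome reports (SAP)**
- Time to event (17.4.1.2, 17.5.9.2, 17.5.14.2, 17.5.16.3.2): hazard ratio with 95% interval.
- Rates (17.5.4.2, 17.5.6.2, 17.5.7.2): rate ratio with 95% interval.
- Binary outcomes (17.5.1.2, 17.5.2.2, 17.5.5.2, 17.5.10.2, 17.5.11.2, 17.5.12.1.2, 17.5.13.2, 17.5.16.1.2, 17.5.16.2.2, and the added analysis in 19.3): relative risk with 95% interval.
- Durations (17.5.8.2, 17.5.15.2): means with intervals, or medians with interquartile ranges.

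Type of organism and type of retinopathy treatment are descriptive only, with no test planned. The two durations are therefore the only tested outcomes without a named between-arm measure.

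**2. Which branch is likely**

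Inputs from the SAP: "The trial population aims to include 858 babies who require the narrowest PICC (Premicath 1" French gauge) in section 8.4, and "Babies will be randomised to AM-PICC or S-PICC in a ratio of 1:1" in section 8.7. So 858 / 2 = 429 per arm.

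Assumed shapes, since the SAP gives none:
- log-normal with median 5 days and log-SD 0.9, rounded;
- gamma with shape 1.2 and mean 1.2 × 6 = 7.2 days, rounded;
- zero-inflated negative binomial.

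A Shapiro-Wilk check on both arms pooled rejected normality in 100% of the 200 samples tried for each shape. Shapiro-Wilk is itself an assumption, because the SAP names no criterion.

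**3. Whether either test is safe if fixed**

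There were 4000 simulated trials per shape with no true effect, at two-sided 5%. The Monte Carlo standard error is √(0.05 × 0.95 / 4000) = 0.0034, or 0.3 percentage points.
- t test: 4.1% to 5.2%.
- Mann-Whitney: 4.5% to 4.9%.

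Both hold their level at this size, even on skewed counts. Non-normality is therefore no reason to avoid an analysis of means.

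**4. What fixing one test may cost in power**

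With durations 15% shorter in one arm:

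| Shape | t test | Mann-Whitney |
|---|---|---|
| Log-normal | 54.7% | 63.6% |
| Gamma | 71.9% | 56.4% |

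Neither test is better throughout. The reduction was applied to days already rounded and then rounded again, which weakens the rank test somewhat. Rounding only once leaves the ordering within each shape unchanged.

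**5. Granularity of a rank-based shift**

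The Hodges-Lehmann estimate is the median of all between-arm differences. With 429 per arm there are 429 × 429 = 184,041 of them. All are whole days and their number is odd, so the estimate is a whole number of days.

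**The case against.** The strongest reply is that this is ordinary shorthand. A two-sample t test normally comes with a mean difference and its interval, and the wording on means does not exclude it. Medians and interquartile ranges by arm do show direction and rough size. These are items 8 and 15 of 16 secondary outcomes, with no multiplicity control claimed. All of this stands and keeps the point minor. It does not supply an effect estimate or interval under Mann-Whitney.

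A reader might infer something stronger: that an unfixed test inflates the type I error. Running both tests and taking the smaller p-value would give 6.6% to 7.9% on the assumed shapes. The SAP does not allow that choice. It selects on the distribution, not on the p-value. When a pooled Shapiro-Wilk rule was simulated on skewed counts, it chose Mann-Whitney every time and the error was 4.9%, with 4.6% to 5.0% in repeat runs. The absent criterion is missing detail, not a source of false positives.

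A reader might also infer that the test would be chosen after seeing results by arm. The SAP does not say whether the distribution is judged pooled or by arm. Sections 15 and 17.1 settle deviations and analysis sets before allocations are requested, and section 19.1.1 mentions a blind review. None of these covers the choice of test, but they give no support to the suspicion either.

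**Conclusion.** The point holds as a minor one. Sections 17.5.8.2 and 17.5.15.2 specify no between-arm estimate with an interval. That is clear under Mann-Whitney. Under the t test it is an unstated intention at best. The two outcomes are alone in this among those formally tested.

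The omission itself is a matter of reading and rests on no assumption. That Mann-Whitney is the likely branch rests on the day counts being right-skewed, which is plausible but not documented in the SAP.

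The consequence is limited to how informative two secondary results will be. The primary analysis is untouched, section 12 contains no defect, and no error-rate inflation follows from the text. Although cost-effectiveness is among the trial's stated aims (section 8.1), nothing in the SAP ties these two durations to it, so no economic consequence is claimed.

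**What to change.** In both sections, delete the clause that makes the test depend on the distribution, and name one analysis with an estimate on the same scale. Either of these would do:

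- **Difference in means:** report the between-arm difference in mean days with a bootstrap 95% interval, and test that same difference. This gives days saved or added directly. The cost is some power where the shape favours ranks, as with the log-normal shape above.
- **Rank-based:** keep the Mann-Whitney test and report the Hodges-Lehmann shift with its 95% interval. The cost is a coarse estimate when whole-day counts are heavily tied.

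The two should not be mixed. A mean difference beside a rank p-value can point in different directions. Keep medians and interquartile ranges by arm as description in either case.

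The change needs a sentence or two in each section and a few lines of code, and no new data.

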17.5.9. Time to PICC removal

17.5.9.1. Derivation

The date of PICC removal is captured on CRF "Form 6: Removal". The date of randomisation

is recorded on CRF "Form 2: Randomisation". The amount of days between randomisation

and PICC removal can be calculated from this. Babies whose parents have withdrawn consent

for the baby to continue in the trial will be censored at the date of last observation if the PICC

is still in situ. Babies who die with the PICC in situ will be censored at date of death.

17.5.9.2. Analysis

The survival analysis will use the method of the Log rank test and Cox proportional hazard

regression models if appropriate. Results will be presented using Hazard Ratios and 95%

confidence intervals. Kaplan-Meier curves stratified by treatment will be presented. Survival

times will be measured from the date of randomisation to the date of PICC removal.

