19.2.3. the line is	Rate of blood/CSF culture sampling per 1000 PICC-days over total time in situ	
19.2.4.	Type of organism grown (clinically serious BSI)	34
19.2.5.	Type of organism grown (from BSI excluding arterial or CVC samples).	34

				•	•	•	•	•	-	pathogenic 34
1 20.	Safety E	valuation	s				 			35 35
	20.2.	Presenta	tion	of the dat	a	•••••	 			35
21. 22. 23.	Appendi	ces					 			36 36 37
	23.2.	Appendix	c II				 			38

5. Statement of Compliance

This Statistical Analysis Plan (SAP) provides a detailed and comprehensive description of the

pre-planned final analyses for the study " $\underline{\mathsf{PREV}}$ enting infection using $\underline{\mathsf{A}}$ ntimicrobial

Impregnated Long lines (PREVAIL)". The planned statistical analyses described within this

document are compliant with those specified in brief within the PREVAIL protocol version 5.0.

This study is carried out in accordance with the World Medical Association Declaration of

Helsinki (1964) and the Tokyo (1975), Venice (1983), Hong Kong (1989) and South Africa

(1996) amendments and will be conducted in compliance with the protocol, Clinical Trials

Research Centre (CTRC) Clinical Trials Unit (CTU) Standard Operating Procedures (SOPs)

and EU Directive 2001/20/EC, transposed into UK law as the UK Statutory Instrument 2004

No 1031: Medicines for Human Use (Clinical Trials) Regulations 2004.

These planned analyses will be performed by the trial statistician. The results of the final

analysis described within this statistical analysis plan will be contained within a statistical

analysis report. This report will be used as the basis of the primary research publications

according to the study publication plan.

All analyses are performed with standard statistical software (SAS version 9.3 or later). The

finalised analysis datasets, programs and outputs will be archived following Good Clinical

Practice guidelines and SOP TM021 Archiving procedure in CTRC. The testing and validation

of the statistical analysis programs will be performed following SOP ST001.

6. Background and Rationale

The rationale for the trial is outlined in the protocol. To summarise, currently antibiotic

impregnated central venous catheters are used in paediatric and adult intensive care.

However, no neonatal units (NNUs) in the UK use antimicrobial impregnated coated

peripherally inserted central catheters (AM-PICCs) (despite the AM-PICCs being CE marked).

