17.4. Analysis of outcomes

17.4.1. Primary Outcome

The primary efficacy outcome is time to BSI based on any positive blood/CSF culture

(including fungal isolates) taken between 24 hours after randomisation until 48 hours after

PICC removal.

17.4.1.1. **Derivation**

The date and time that a sample was taken is recorded on CRF "Form 5: Microbiology". The

samples included for the primary outcome are those taken between 24 hours after

randomisation until 48 hours after PICC removal. The date and time of randomisation can be

found on CRF "Form 2: Randomisation". The date and time of PICC removal can be found on

CRF "Form 6: Removal". The unit of measurement will be hours.

BSI is defined as any positive culture recorded on CRF "Form 5: Microbiology" for the field

"organism cultured" (any culture except an entry of 'none') from blood or CSF samples. Any

'other' recorded organism will be referred to the clinical team for confirmation of whether this

is a positive culture. Organisms grown from 'other' sample types will also be referred to the

clinical team for confirmation of whether this constitutes the primary outcome.

All decisions made by the clinical team, will be made blinded to treatment allocation.

If there is a positive culture prior to the primary outcome time window and a positive culture in

the primary outcome time window:

• If the second positive culture is from the same isolate as the first and:

o there were less than 14 days between the two samples they should be

classified as the same episode of BSI and the positive culture within the primary

outcome time window will not be counted.

o there were 14 days of more between the two samples they should be classified

as two independent episodes of BSI and the positive culture within the primary

outcome time window will be counted.

If the second positive culture is from a different isolate to the first and:

o there were less than 24 hours between the two samples they should be

classified as the same episode of BSI and the positive culture within the primary

outcome time window will not be counted.

o there were 24 hours or more between the two samples they should be classified

as two independent episodes of BSI and the positive culture within the primary

outcome time window will be counted.

If there are multiple positive cultures within the primary outcome time window, each positive

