17.5.4. Rate of BSI per 1000 PICC-days (including recurrent BSI)

17.5.4.1. Derivation

BSI is as defined in section 17.4.1.1. Where there are multiple positive cultures in the POTW,

independent episodes of BSI will be classified as in section 17.5.3.1. The total number of

independent episodes of BSI that occur when the line is in situ during the POTW should be

calculated for each baby and then summed to find the total number of BSI in each treatment

arm.

The number of days that the PICC is in situ for during the POTW can be calculated by

subtracting the date and time of the start of the POTW (Date and time of randomisation + 24

hours) from the date and time of PICC removal (or date and time of death if the baby died with

the line in situ). The date and time of PICC removal can be found on CRF "Form 6: Removal"

under section 1. The number of days should be summed to find the total number of days that

the PICC is in situ for during the POTW in each arm. For babies that did not have a line

inserted, this will be zero.

The rate of BSI per 1000 PICC-days is calculated as:

Total number of independent episodes of BSI that occur when line is in situ during POTW, across treatment arm $\times 1000$ Total number of days PICC is in situ for during the POTW (across treatment arm)

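### Time to PICC removal (SAP 17.5.9) is counted in whole days although clock times are held, and no tie method is named for the heavily tied Cox model that results

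*SAP*

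**What the plan says.** Two parts of section 17.5.9 set the time scale. The derivation (17.5.9.1) states that "The date of PICC removal is captured on CRF" Form 6, takes the date of randomisation from Form 2, and counts the days between the two. A baby who dies with the line in place is censored at the date of death, and a withdrawn baby at the date of last observation. The analysis (17.5.9.2) repeats that survival "times will be measured from the date of randomisation to the date of PICC removal" and plans a log-rank test, Kaplan-Meier curves and, if appropriate, a Cox model with a hazard ratio and 95% interval. It does not say how ties are handled.

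Elsewhere the SAP uses the same forms at finer resolution:

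- 17.4.1.1 (primary outcome): "The date and time of randomisation can be" found on Form 2, "The date and time of PICC removal can be found on" Form 6, and "The unit of measurement will be hours". The date and time of death are on Form 7a.
- 17.5.4.1 (PICC-days): "The date and time of PICC removal can be found on CRF" Form 6, and the clock time of removal or death enters the denominator.
- 17.3 tabulates lines removed less than 24 hours after randomisation, which strictly needs clock times at both ends.
- Section 18 imputes a missing time as 12:00 when the date is known.

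Section 5 names the software as SAS 9.3 or later.

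**The concern.** The SAP gives no reason for coarsening this one outcome when the finer fields are already being derived for others. Section 8.4.3 says that every baby's line is removed at some point, so almost every baby is an event. Those events fall on a short scale of whole days, so ties are unavoidable and heavy.

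Under heavy ties the Cox estimate depends on the approximation chosen, and the SAP leaves that choice open. Breslow's approximation pulls the coefficient towards zero. Efron's approximation and exact methods largely avoid this. As general software knowledge, not stated in the SAP, the named package applies Breslow unless another method is requested. An analyst who writes the model as the SAP describes it could therefore report a slightly weakened hazard ratio and interval without having made a decision. Near the 5% threshold, the log-rank p-value and the Cox interval could then point in different directions.

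**Working it through.** The SAP gives no event count, effect size or power for this outcome, so there is no figure to reproduce. The check is a simulation.

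**Inputs from the SAP.** 858 babies (8.4); 1:1 allocation (8.7), so 429 per arm; two-sided 5% level (section 12).

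**Assumptions, because the SAP gives no dwell-time distribution.** Weibull removal times with median 4, 8 or 12 days and shape 1 or 1.5; true HR 0.80 or 1.25; no censoring; randomisation clock time uniform from 08:00 to 20:00; 200 trials per scenario. With t the dwell in days and c the clock time as a fraction of a day, the calendar-date difference is d = floor(c + t).

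Each simulated trial was analysed three ways: Cox on clock times, Cox on d with Breslow ties, and Cox on d with Efron ties. The last two columns give the mean log HR from dates divided by the mean log HR from clock times.

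| True HR | Median, shape | Clock HR | Dates, Breslow | Dates, Efron | Largest tie | Ratio, Breslow | Ratio, Efron |
|---|---|---|---|---|---|---|---|
| 1.25 | 4, 1 | 1.261 | 1.235 | 1.260 | 140 | 0.912 | 0.998 |
| 1.25 | 4, 1.5 | 1.244 | 1.209 | 1.242 | 138 | 0.868 | 0.994 |
| 1.25 | 8, 1 | 1.236 | 1.223 | 1.235 | 79 | 0.952 | 0.997 |
| 1.25 | 8, 1.5 | 1.252 | 1.233 | 1.252 | 75 | 0.931 | 0.997 |
| 1.25 | 12, 1 | 1.243 | 1.234 | 1.243 | 57 | 0.968 | 0.999 |
| 1.25 | 12, 1.5 | 1.250 | 1.237 | 1.249 | 53 | 0.953 | 0.998 |
| 0.80 | 4, 1 | 0.799 | 0.812 | 0.799 | 117 | 0.927 | 0.998 |
| 0.80 | 4, 1.5 | 0.794 | 0.815 | 0.795 | 121 | 0.887 | 0.996 |
| 0.80 | 8, 1 | 0.798 | 0.805 | 0.798 | 65 | 0.962 | 0.999 |
| 0.80 | 8, 1.5 | 0.799 | 0.810 | 0.799 | 66 | 0.940 | 0.997 |
| 0.80 | 12, 1 | 0.802 | 0.806 | 0.802 | 47 | 0.975 | 1.000 |
| 0.80 | 12, 1.5 | 0.794 | 0.802 | 0.794 | 47 | 0.960 | 0.999 |

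**Ties.** The 858 babies fall on about 18 to 86 distinct values, with 47 to 140 on the commonest day.

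**Shrinkage with Breslow.** It runs from 1 − 0.975 = 2.5% to 1 − 0.868 = 13.2% of the log HR. Applied to a true 1.25 (log 0.2231), the HR 1.25 scenarios give exp(0.868 × 0.2231) = 1.21 to exp(0.968 × 0.2231) = 1.24.

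**Shrinkage with Efron.** The ratio is 0.994 to 1.000, so there is none of practical size.

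**Log-rank test.** Power on clock times and on dates differs by at most one percentage point in every scenario (for example 0.910 against 0.915 at HR 0.80, median 8, shape 1.5). At HR 1 (400 trials) the rejection rate was 0.068 against 0.065.

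**Zero times.** Same-day removals made up 0.4% to 7.8% of babies. Dropping them changed the Breslow HR by no more than 0.003.

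**Scale against sampling error.** With 858 events, SE(log HR) ≈ 2/√858 = 0.068. A shift from 1.25 to 1.23 is 0.2231 − 0.2070 = 0.016, about a quarter of a standard error. The largest shrinkage, 0.132 × 0.2231 = 0.029, is a little under half of one.

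**The case against.** The strongest reply is that dates are not the cause. With Efron ties, dates reproduce the clock-time estimate almost exactly, so the whole effect belongs to Breslow's method, and neither that method nor any software default appears in the SAP. This stands, and it makes the point conditional: the SAP leaves open a setting that matters once times are in whole days. It does not plan a biased analysis.

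Three stronger readings are tempting and should not be drawn:

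- *Information is lost by using dates.* A separate simulation (400 runs, shape 1, HR 1.25) gave a mean Wald z of 3.31 with clock times and 2.96 with dates and Breslow at a mean dwell of 5 days. The squared ratio, (2.96/3.31)² = 0.80, looks like a 20% loss. But dates with Efron gave 3.28, and log-rank power barely moves. The drop is Breslow shrinkage.
- *Zero times do harm.* They are few under the assumed dwell times and have almost no effect on the estimate.
- *The hazard ratio will be biased.* It will be only if Breslow is used and there is a true difference; at HR 1 all three analyses agreed (1.003 to 1.004).

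A further objection is that clock times bring small problems of their own. A baby randomised at 15:00 and removed the same day with no recorded time would be given 12:00 − 15:00 = −3 hours under section 18, and withdrawals are described by date only. This also stands, and a one-line rule answers it.

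**Conclusion.** The point holds in its conditional form. Section 17.5.9 uses a coarser time scale than the recorded data allow and names no tie method for a Cox model with heavy ties. If Breslow ties are used, the reported log hazard ratio is weakened by about 2.5% to 13%. That shift is small beside its standard error and goes towards no difference. Efron ties remove it, and the log-rank test is essentially unaffected either way. The sizes rest on assumed dwell times, assumed randomisation hours, no censoring, and true hazard ratios of 0.80 and 1.25. This is a minor point on one of 16 listed secondary outcomes, worth correcting because the correction is nearly free.

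**What to change.** In 17.5.9.1 and 17.5.9.2, measure from the date and time of randomisation to the date and time of removal, or of death for babies censored with the line in place, in hours as in 17.4.1.1. Apply the section 18 rule of 12:00 to missing times, and set any resulting time of zero or less to a stated small positive value. Name Efron (or exact) ties for whatever ties remain, including those from withdrawal times known only by date.

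The cost is a few lines of SAP text and one derived variable from fields already used elsewhere. No new data are needed. The only downside is a few imputed times, and section 18 already requires the number of babies with imputation to be reported.
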